Study Design	
A randomized, open-label, 2-arm parallel study comparing glycemic control, patient satisfaction, and quality of life (QOL) of using Finesse versus pen to initiate and manage bolus insulin dosing in 312 patients, male and female, ages 22 to 75 years of age with T2DM not achieving glycemic targets on basal insulin with/without AHA. After a 4-week screening/baseline period, patients will be randomized 1:1 (balanced by study center) to either the Finesse arm or the pen arm to initiate bolus insulin using a simple bolus dosing algorithm and followed for a 44-week intervention period. After the final endpoint evaluation at week 44, patients will crossover to the alternate bolus insulin delivery device for 4 weeks and complete a patient preference survey at week 48.
 
The study will be conducted in the following periods: Screening Visit 1 (Week -4 to -3); Baseline Visit 2A (Week -2); Randomization Visit 3 (Week 0) to include insulin dosage optimization;i,1 Phone Calls Insulin Titration (Weeks 1, 2, 3, 6, 8); Follow-up Visits 4 (Week 4), 5 (Week 12), 6C (Week 24), 7 (Week 36), 8 (Week 44), and 9 (Week 48). Visits 2B (Week -1), 6A (Week 22), and 6B (Week 23): Only the subset of patients performing continuous glucose monitoring (CGM) (50 patients per arm) will have additional visits for performing blinded CGM assessments.

Study Sites	A multicenter study (approximately 50 sites). Sites and patients will be approximately divided between the US and EU.
Patient Population	A total of approximately 312 enrolled adults, male and female, aged 22-75 years, body mass index of $\leq 40 \text{ kg/m}^2$ , with T2DM not achieving glycemic targets (A1C 7.5-11.0%)

i Educational materials specifically designed for this study based on the International Diabetes Center simple algorithm for adjustment of insulin in Type 2 diabetes. Patients will record SMBG before meals and bedtime, and insulin doses.

	using basal insulin ( $\geq 0.3$ U/kg/day) with/without AHA based on the participant's medical needs.
Duration of Patient Participation	Total duration of participation by each patient is expected to be approximately 52 weeks.

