Dosage and Administration	
At randomization, total daily dose (TDD) of insulin will be divided as 50:50, basal: bolus (Note: For those subjects with a screening A1C of <math><9\%</math>, the TDD is to be reduced by 10% prior to splitting the dose 50:50, basal: bolus, in order to avoid potential for hypoglycemia at institution of new regimen). Basal insulin therapy for each group will be titrated using a simple algorithm by chart to adjust by 2U increments to achieve pre-morning meal fasting plasma glucose (FPG) target of 71-130 mg/dl (4.0-7.2 mmol/l). Bolus insulin dosing will start with fixed pre-meal doses (divided equally between morning meal, midday meal, and evening meal). Prandial insulin therapy for each group will be titrated using a simple algorithm by chart to adjust by 2U increments based on pre-midday meal and pre-evening meal self-monitoring blood glucose (SMBG) target of 71-130 mg/dl (4.0-7.2 mmol/l) and bedtime SMBG target of 71-130 mg/dl (4.0-7.2 mmol/l): pre-morning meal dose will be titrated based on pre-midday meal SMBG; pre-midday meal dose will be titrated based on pre-evening meal SMBG; pre-evening meal dose will be titrated based on bedtime SMBG. For basal insulin, all patients will use Lantus® (Glargine) by a pen (SoloStar®) before evening meal or at bedtime. For bolus insulin, patients will use Finesse containing rapid-acting NovoLog®/NovoRapid® (Aspart) or the FlexPen®. Patients will discontinue the following AHA: Sulfonylureas, Meglitinides, GLP-1 agonists, bromocriptine, and DPP-4 inhibitors that have not been studied in combination with insulin, namely, saxagliptin and linagliptin. Patients on the following AHAs will continue them in their current doses: Biguanides, Alpha-glucosidase inhibitors, SGLT2 inhibitors, Thiazolidinediones, and DPP-4 inhibitors that have been studied and approved for use in combination with insulin, namely, sitagliptin, alogliptin, and vildagliptin.

Endpoint Evaluation at Week 24	
Primary Endpoint	Change in A1C from baseline to week 24, comparing Finesse versus Pen.
Secondary Endpoints	
 
• Proportion of patients with A1C <math>\leq 7.0\%</math> at week 24;
 

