	
 
• Change in percent of glucose values of CGM measurements (in a subset of patients) within targeted range of 71 and 180 mg/dl (4.0 and 10.0 mmol/l) from a one or two week period of week -2 to week 0 (baseline) to a one or two week period of week 22 to week 24;
 
• Change in 3-day average 7-point SMBG from baseline to week 24;
 
• Change in 3-day coefficient of variation (CV) of 7-point SMBG from baseline to week 24;
 

Tertiary Endpoints	
 
• Change in A1C from baseline to week 12;
 
• Change in average glucose values of CGM measurements (in a subset of patients) from a one or two week period of week -2 to week 0 (baseline) to a one or two week period of week 22 to week 24.
 
• Change in percent of glucose values of CGM measurements (in a subset of patients) <math>\leq</math> 70 mg/dl (<math>\leq</math> 3.9 mmol/l) and percent of values <math>></math> 180 mg/dl (<math>></math> 10.0 mmol/l) from a one or two week period of week -2 to week 0 (baseline) to a one or two week period of week 22 to week 24;
 
• Change in FPG from baseline to week 24;
 
• Change in 3-day insulin doses (total daily dose, basal dose, bolus dose) from baseline to week 24.
 

Patient Reported Outcomes	
 
• Change in treatment satisfaction for insulin delivery from baseline to week 24;
 
• Change in patient quality of life from baseline to week 24;
 
• Patient experience survey at week 24;
 
• Patient insulin usage survey at week 12 and 24.
 

Healthcare Provider Reported Outcomes	
 
• HCP experience survey at week 24.
 

Endpoint Evaluation at Week 44	
Secondary Endpoints	
 
• Change in A1C from baseline to week 44;
 
• Proportion of patients with A1C <math>\leq</math> 7.0% at week 44;
 
• Change in 3-day average 7-point SMBG from baseline to week 44;
 
• Change in A1C from week 24 to week 44.
 

Tertiary Endpoints	
 
• Change in A1C from baseline to week 36;
 
• Change in 3-day CV of 7-point SMBG from baseline to week 44.
 
• Change in FPG from baseline to week 44;
 

	
 
Change in 3-day insulin doses (total daily dose, basal dose, bolus dose) from baseline to week 44.
 

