#### Efficacy Analysis Plan

Differences between arms (Finesse arm versus pen arm) at week 24 will be analyzed using analysis of covariance (ANCOVA) model with the baseline A1C value as the covariate; the 2-sided 95% confidence interval of the difference will be computed using the model. The non-inferiority of Finesse to pen will be concluded if the upper bound of the 95% 2-sided confidence interval for change in A1C is less than the inferiority margin of 0.4%. This test is the same as a 1-sided test with an alpha of 0.025. Superiority of Finesse will be tested if non-inferiority is shown.

Each of the secondary and tertiary endpoints at week 24 and week 44 will be tested for superiority of the Finesse arm to the pen arm, but the tests will be interpreted inferentially only if non-inferiority is demonstrated with respect to the primary endpoint. Otherwise, the p-values and 95% confidence intervals for the secondary and tertiary endpoints will be considered to be nominal. The continuous endpoints will be analyzed using the same ANCOVA model described for the primary endpoint. The categorical endpoints will be analyzed using a Cochran-Mantel-Haenszel test. The Type 1 error rate will be at 0.05.

To evaluate durability of effect of using Finesse versus pen, change in A1C from 24 week to 44 week will be analyzed by treatment groups using t-test for each treatment arm.

Other general considerations for the statistical analysis will include descriptive statistics (sample size, mean, SD, median, minimum, and maximum) for continuous variables and 95% CI of the mean, and, where appropriate, the percentage values for categorical variables, and tests of significance between treatment arms including p-value and 95% CI.

Additional Analyses

Analyses will also be performed to examine the relationships between variables known to be associated. In particular, the relationship between A1C and severe hypoglycemiaiii, the relationship between A1C and weight change, and the relationship between A1C and adherence measures will be described in each group. These analyses will be descriptive, primarily using categorical cross-classifications to examine whether any shifts in hypoglycemia, weight change, or adherence measures are consistent with expected changes due to improved glycemic control.

---

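### The A1C ≤7.0% responder endpoints get a Cochran-Mantel-Haenszel test with no strata named, so baseline A1C, which the continuous analyses adjust for, is not used

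*Combined protocol and SAP*

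**What the plan says.** Under Secondary Endpoints, the week-24 list opens with a responder endpoint, "Proportion of patients with A1C" at or below 7.0%. The week-44 list repeats it. The Efficacy Analysis Plan tests each secondary endpoint for superiority of Finesse and treats the result as inferential only if non-inferiority is shown on the primary endpoint.

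For this endpoint the method is given in one sentence: "The categorical endpoints will be analyzed using a Cochran-Mantel-Haenszel test". No stratification factor, covariate or effect measure is named, although the same section expects confidence intervals for secondary endpoints. On error rate it says "The Type 1 error rate will be at 0.05".

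Continuous endpoints are treated differently. They use an "analysis of covariance (ANCOVA) model with the baseline A1C value as the covariate".

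Patient Population sets entry A1C at 7.5 to 11.0%. Study Design says that randomisation is balanced by center. Analysis Sets summarises efficacy in mITT and PP, with mITT for the primary efficacy analyses. A patient belongs to mITT with a baseline A1C and any one later A1C, so a week-24 or week-44 value is not required. No section says how a missing value counts in the responder endpoint.

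**The concern.** Whether a patient reaches a fixed threshold depends on where that patient starts. The plan accepts this logic for continuous endpoints but does not carry it over to the responder endpoint built from the same A1C measurement. A test that ignores an informative baseline variable remains valid in a randomised trial, but it is less sensitive than it could be. Chance imbalance in baseline A1C between arms also passes straight into the observed difference in proportions.

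At stake is some power, and some precision of the estimate, on the first-listed week-24 secondary endpoint and its week-44 repeat. The data are already collected and already used elsewhere in the analysis, so the improvement is nearly free.

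A second, smaller gap sits beside it. With 20% discontinuation assumed by week 24 and no figure for week 44, the handling of patients without a value can change the reported difference if dropout differs by arm.

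**Working it through.** **1. The plan's own figure.** Sample Size Determination concerns only the primary test. Inputs: margin 0.4, true difference -0.1, SD 1.2, one-sided 0.025, power 90%. Per arm, n = 2 × 1.2² × (1.960 + 1.282)² / (0.4 + 0.1)² ≈ 121.0, rounded up to 122, or 244 in total against 250 stated. Power at 125 per arm is 0.909. Inflation: 250/0.80 = 312.5, stated as 312. The figure reproduces. No response rate or power is given for the responder endpoint, so everything below rests on assumed rates.

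**2. Distance to target.** 7.5 - 7.0 = 0.5 points at the lower entry limit and 11.0 - 7.0 = 4.0 points at the upper.

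**3. What using baseline A1C gains.** There were 2,000 simulated trials per setting.
- From the plan: 125 per arm, baseline limited to 7.5-11.0%, alpha 0.05 (read as two-sided).
- Assumed: baseline normal with mean 8.7 and SD 0.9 before truncation; week-24 SD 1.0; effect 0.4; correlation r of baseline with week-24 A1C, before truncation, of 0.2, 0.4 or 0.6.
- Model: week-24 A1C = 7.5 - 0.4 × arm + r × (1.0/0.9) × (baseline - 8.9) + error, with error SD √(1 - r²). A responder has week-24 A1C ≤ 7.0.
- Baseline bands for stratified CMH are cut at 8.0, 8.5, 9.0 and 9.5.

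This gives about 31% responders on pen and 46 to 48% on Finesse. Power:

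| r | CMH, no strata | CMH, baseline bands | Logistic with baseline |
|---|---|---|---|
| 0.2 | 0.693 | 0.702 | 0.702 |
| 0.4 | 0.714 | 0.740 | 0.755 |
| 0.6 | 0.734 | 0.807 | 0.812 |

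The gain from logistic regression is about 1, 4 and 8 points. Baseline bands give about 1, 3 and 7. The simulation standard error of one power figure is √(0.7 × 0.3/2000) ≈ 0.010, so the gain at r = 0.2 is negligible. With no treatment effect (r = 0.4) the rejection rates were 0.055, 0.050 and 0.053, so Type 1 error is held by all three.

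A second set, with effects of 0.3-0.4%, SD of change 1.0-1.2 and a baseline slope of -0.3 to -0.5, gave unadjusted v adjusted power of 0.46 v 0.50, 0.29 v 0.32, 0.54 v 0.56, 0.38 v 0.41 and 0.44 v 0.46: gains of 2 to 4 points.

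At the plan's own difference of 0.1%, simulated power was about 8 to 9% for CMH and logistic regression alike, so the choice hardly matters there.

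**4. Could the unnamed strata be centers?** Center is the only balancing factor named. About 312/50 ≈ 6 patients per site makes sparse strata, and they still carry no baseline A1C.

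**5. Missing values.** Assume 25% responders on pen and 40% on Finesse among those observed.
- Equal 20% dropout: power is 0.81 if all 156 per arm are observed, 0.72 on observed cases (125 per arm), and 0.68 with missing counted as not at target.
- Dropout 30% Finesse, 10% pen: observed cases keep 15 points; missing as not at target gives 0.40 × 0.70 - 0.25 × 0.90 = 0.055, or 5.5 points.
- Dropout 15% Finesse, 25% pen: 0.40 × 0.85 - 0.25 × 0.75 = 0.1525, or 15.3 points.

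The two rules can therefore differ widely or hardly at all, depending on the dropout pattern.

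**The case against.** The strongest reply is that CMH is by construction a stratified test, so leaving the strata unnamed is silence and not a decision against baseline A1C. An analyst could choose baseline bands and do about as well as with logistic regression. That stands, and it is why banded CMH is an acceptable remedy. But nothing in the plan commits to it, and the two readings nearest the text, no strata or center strata, both leave baseline A1C out.

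The second reply is that the gain is modest and rests on effects of 0.3-0.4%, three to four times the difference that the plan assumes. That also stands.

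A reader might infer three stronger things that the documents do not support.
- That the test as written drops patients with no value at the visit. No section says so. The mITT definition admits such patients and fits carrying a value forward, or counting missing as failure, equally well. Only patients with no post-baseline A1C at all are outside both efficacy sets by definition.
- That counting missing as not at target would restore power. Under equal dropout it costs power (0.72 to 0.68). Combined with logistic regression at 156 per arm and 20% dropout, it gave 0.274, 0.381, 0.457 and 0.610, against 0.296, 0.400, 0.456 and 0.638 for CMH on observed cases. It also mixes retention with glycemic response, which is a choice of estimand and not a correction.
- That the plan hides differential dropout. Discontinuation due to adverse events is listed under Safety Observations, though an all-cause comparison by arm is not. A gap in dropout need not alter the conclusion either: with 40% responders observed in both arms and 25% v 15% missing, the rates become 30% v 34%, which at 156 per arm has p of about 0.45.

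**Conclusion.** The point holds as a missed, nearly free improvement on a secondary endpoint. As specified, the responder test makes no use of baseline A1C. Using it would add about 1 to 8 points of power at 125 per arm with an assumed effect of 0.4%, 2 to 4 points in the second set of settings (0.3-0.4%), and almost nothing at the plan's -0.1%. The size depends mainly on how strongly baseline predicts week-24 A1C, which the documents do not give; the range shown is for correlations of 0.2 to 0.6. The planned test is valid, and the primary non-inferiority analysis is untouched.

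The absence of a missing-value rule for this endpoint is a secondary note. It is a question of estimand and possible bias, and it matters only to the extent that dropout differs between arms.

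**What to change.** In the Efficacy Analysis Plan, specify for the week-24 and week-44 responder endpoints either of the following:
- logistic regression on arm and baseline A1C, reporting a baseline-standardised risk difference with 95% CI; or
- CMH stratified by baseline A1C bands fixed in advance.

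Keep unstratified CMH as a sensitivity analysis.

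Also state one rule for a missing week-24 or week-44 A1C (observed cases, or missing as not at target) and report the other as a sensitivity analysis.

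The cost is a few sentences in the plan and trivial programming, with no new data. If missing is counted as not at target, reported response rates fall and, with equal dropout, so does power slightly; that should be accepted knowingly when the rule is chosen.

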## STUDY PROTOCOL AND STATISTICAL ANALYSIS

Title of Study	Glycemic Control and Treatment Satisfaction Using Finesse Versus Pen for Initiating Bolus Insulin Dosing in Patients with Type 2 Diabetes Mellitus (T2DM) not Achieving Glycemic Targets on Basal Insulin With/Without Anti-Hyperglycemic Agents (AHA)
Devices	
 
• Finesse Bolus Insulin Delivery System cleared for commercialization in United States (US), Europe (EU), and Canada
 
• FlexPen® (aspart)
 
• SoloStar® Pen (glargine)
 

Study Purpose	In order to enable the Healthcare Provider (HCP) to more easily advance patients with T2DM sub-optimally controlled on basal insulin therapy to basal and bolus therapy, a novel bolus insulin patch ("Finesse") was developed by the Sponsor. The proposed study aims to determine whether initiating and managing bolus therapy with Finesse will result in non-inferior or improved glycemic control in patients with T2DM compared with a pen.

Study Objectives	
Primary Objective:
 
To compare the change in A1C, with bolus insulin dosing with Finesse versus pen, from baseline to the completion of 24 weeks of basal and bolus insulin therapy.
 
Secondary Objectives:
 
 
• To compare the change in other parameters of glycemic control with bolus insulin dosing with Finesse versus pen, from baseline to the completion of 24 weeks and 44 weeks of basal and bolus insulin therapy.
 
• To demonstrate that patient reported outcomes (PRO) improve with Finesse versus pen following the completion of 24 weeks and 44 weeks of basal and bolus insulin therapy.
 
• To demonstrate that HCPs prefer Finesse to pen for initiation of bolus insulin therapy following the completion of 24 weeks of basal and bolus insulin therapy by the last patient at their investigative site.
 

------------------	--

	
 
• To demonstrate the durability of effect of using Finesse and pen on maintenance of A1C from week 24 to week 44 of basal and bolus insulin therapy.
 
• To demonstrate that patients prefer Finesse to pen for bolus insulin therapy following a 4-week crossover from week 44 to week 48.
 

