Patient Reported Outcomes	
 
Patient experience survey at week 44;
 
Patient insulin usage survey at week 36 and 44.
 

Endpoint Evaluation at Week 48	
Patient Reported Outcomes	
 
Patient preference survey at week 48.
 

Safety Observations	
 
Incidence and rate of severe hypoglycemiaii,3
 
Incidence and rate of non-severe hypoglycemia (<math>\leq 70</math> mg/dl) (<math>\leq 3.9</math> mmol/l) (both symptomatic and asymptomatic);
 
Incidence of all adverse events;
 
Incidence of serious adverse events;
 
Incidence of adverse device effects;
 
Incidence of serious adverse device effects;
 
Discontinuation rate due to adverse events.
 
Incidence of clinically important changes in clinical laboratory tests, vital signs (pulse, blood pressure), physical examination, and body weight.
 

Data Analysis	
Analysis Sets
 
The intent-to-treat (ITT) analysis set includes all patients who initiated bolus insulin therapy. The modified intent-to-treat (mITT) analysis set includes all the ITT patients who had a baseline and at least one post-baseline A1C measurement. The per protocol (PP) analysis set consists of all mITT patients who complete the 24-week efficacy phase, and have no major protocol deviations that may affect the interpretation of the primary efficacy endpoint. Efficacy measurements will be summarized for both mITT and PP analysis sets; the primary efficacy analyses will be based on the mITT analysis set. The ITT set will be used for all safety analyses.
 
Sample Size Determination

ii Severe hypoglycemia is defined as an event requiring the assistance of another person to actively administer carbohydrate (including IV dextrose), glucagon, or other resuscitative actions. These episodes may be associated with sufficient neuroglycopenia to induce seizure or coma. Neurological recovery attributable to the restoration of plasma glucose to normal is considered sufficient evidence that the event was induced by a low plasma glucose concentration.

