The sample size determination is based on the primary endpoint, A1C change from baseline to Week 24. Assuming that the true mean difference in A1C change (Finesse vs Pen) is -0.1% with a SD 1.2%, a study population of 250 completers (125 per arm) is required to achieve a power of 90% for non-inferiority with a margin of 0.4%, i.e., the upper bound 2-sided 95% confidence interval of the difference in mean A1C change (Finesse vs Pen) is less than 0.4%. Assuming a discontinuation rate of 20% (for the 24 week primary endpoint analysis), the number of patients to be enrolled =  $250/(1-0.20) = 312$  patients (156 per arm).

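### The week 24 to week 44 durability t-test has no rule for missing A1C and leaves the week-36 value unused, so it can overstate maintenance if patients who lose control are the ones who leave

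*Combined protocol and SAP*

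**What the plan says.** All references are to the combined protocol and SAP.

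- **Objective.** A secondary objective under Study Objectives reads "To demonstrate the durability of effect of using Finesse and pen on maintenance of A1C from week 24 to week 44".
- **Endpoint.** Endpoint Evaluation at Week 44 lists "Change in A1C from week 24 to week 44" as a secondary endpoint. The same section has "Change in A1C from baseline to week 36" as a tertiary endpoint, so an A1C between the two durability time points is scheduled.
- **Method.** The durability paragraph of the Efficacy Analysis Plan says "change in A1C from 24 week to 44 week will be analyzed by treatment groups using t-test for each treatment arm". For secondary and tertiary endpoints generally, the same section says "The continuous endpoints will be analyzed using the same ANCOVA model described for the primary endpoint", so a between-arm comparison of this change is also planned.
- **Analysis sets.** The mITT set is "all the ITT patients who had a baseline and at least one post-baseline A1C measurement". The PP set is "all mITT patients who complete the 24-week efficacy phase", with a further condition on major deviations. Neither requires a week-44 value.
- **Dropout.** Sample Size Determination states "Assuming a discontinuation rate of 20% (for the 24 week primary endpoint analysis". No figure is given for weeks 24 to 44.

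The plan specifies no imputation, no repeated-measures model, no A1C collection after discontinuation and no sensitivity analysis for missing values.

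**The concern.** A change score needs both of its ends. With no rule for a missing value, a t-test on the week 24 to week 44 change is an analysis of complete pairs. It answers how A1C moved among those who still had a week-44 measurement, whereas the objective concerns maintenance after week 24 in each arm.

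The two questions differ if leaving is related to A1C. In a durability analysis, a patient who leaves because control has slipped is a failure of durability, and dropping that patient moves the mean towards no change. The week-36 A1C could show whether a later leaver was already drifting, but the t-test does not use it.

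Two features raise the stakes. The plan sets no margin for maintenance, so a non-significant rise could be read as durability, and both fewer pairs and selective loss favour that reading. The trial is also open-label, so loss after week 24 could differ between the arms.

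**Working it through.** **1. The plan's own figure.** No sample size, power or dropout figure is given for durability. The primary sample size supplies the starting number at week 24. With margin 0.4, true difference -0.1, SD 1.2, one-sided alpha 0.025 and 90% power, n per arm = 2 x 1.2² x (1.960 + 1.282)² / 0.5² = 121.0, rounded up to 122. The plan states 125 (power 90.9%). 250 / 0.80 = 312.5, against a stated 312. The figures reproduce, so 125 per arm at week 24 is used below.

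**2. Form of the bias.** Let q be the share of week-24 completers with no week-44 A1C, and D the leavers' mean change minus the stayers' mean change. The mean over everyone is (1 - q) x stayers + q x leavers, so the complete-pair mean is too low by q x D. The documents give neither q nor D, so ranges are assumed:

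| q | pairs of 125 | D = -0.5 | D = 0 | D = 0.3 | D = 0.5 | D = 1.0 | CI half-width, SD 0.8 |
|---|---|---|---|---|---|---|---|
| 5% | 119 | -0.025 | 0 | 0.015 | 0.025 | 0.05 | 0.145 |
| 10% | 112 | -0.05 | 0 | 0.03 | 0.05 | 0.10 | 0.150 |
| 15% | 106 | -0.075 | 0 | 0.045 | 0.075 | 0.15 | 0.154 |
| 20% | 100 | -0.10 | 0 | 0.06 | 0.10 | 0.20 | 0.159 |

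Positive entries mean that maintenance is overstated, negative entries that it is understated.

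**3. Simulation with loss after week 36.** All A1C inputs are assumed:
- A1C SD 1.0; correlations 0.75 (weeks 24-36), 0.68 (24-44) and 0.80 (36-44). The SD of the change is then √(2 - 2 x 0.68) = 0.80.
- True mean rise 0.12 at week 36 and 0.20 at week 44.
- Logistic dropout on the week 24 to 36 rise, slope 0.75 (moderate) or 1.5 (strong) per 1 A1C point. These are odds ratios of exp(0.75) = 2.1 and exp(1.5) = 4.5.
- The 17% loss applies the plan's 20% over 24 weeks as a constant hazard: 1 - 0.8^(20/24) = 17.0%, about 42 of 250.

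| Loss | Understatement, moderate | Understatement, strong |
|---|---|---|
| 5% | 0.014 | 0.028 |
| 10% | 0.026 | 0.051 |
| 17% | 0.045 | 0.083 |

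Repeat runs agree to within 0.003. At 17% loss about 104 pairs remain, the standard error is about 0.8 / √104 = 0.078, and the bias is 0.6 to 1.1 standard errors. The chance that the t-test detects the true 0.20 rise is about 0.72 with unrelated loss, 0.50 with moderate dependence and 0.33 with strong dependence. A likelihood estimate that also uses week 36 has bias of 0.002 or less here.

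**4. The same loss spread over weeks 24 to 44.** Step 3 suits the likelihood estimate, because every leaver has a week-36 value. Under the same constant hazard, 1 - 0.8^(12/24) = 10.6% leave before week 36, which is 10.6 / 17.0 = 62% of the leavers. If their leaving depends on the same rise, now unrecorded, the complete-pair bias is 0.047 (moderate) and 0.086 (strong). The likelihood bias is 0.022 to 0.024 and 0.042. About half remains (0.022 / 0.047 = 47%; 0.042 / 0.086 = 49%).

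**The case against.** The strongest reply is that nothing in the documents shows which way the bias runs. No reason for leaving after week 24 is given. Patients could leave for reasons unrelated to A1C, or after hypoglycemia while well controlled, and then the bias is zero or reversed. This stands: a reader might infer that the t-test will make maintenance look better than it is, but the plan supports only that it can.

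A reader might also count the assumed 20% lost before week 24 (about 62 of 312) as part of the bias. Those patients have no week-24 control to maintain. Their absence narrows the population, but nothing shows that it shifts the week 24 to 44 change.

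Third, the bias in the simulation is smaller than the CI half-width, and every A1C input is assumed. That also stands, although a systematic shift of 0.6 to 1.1 standard errors still lowers the chance of seeing a real deterioration.

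Fourth, the per-arm t-test is not the only long-term evidence. The between-arm ANCOVA covers the same change, and baseline-to-week-44 A1C and the proportion at or below 7.0% at week 44 are also analysed. These analyses have no missing-data rule either, and none of them estimates maintenance within an arm.

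Finally, a t-test does not forbid imputation. True, but none is specified. Nor does the method require patients to have stayed on their assigned device; it requires only the two A1C values.

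**Conclusion.** The point holds as a weakness in the analysis of a named secondary objective. The plan prescribes a complete-pair t-test, has no rule for missing A1C and leaves the week-36 value out, although a better method could use data already scheduled.

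The result is conditional on having a week-44 A1C. It may overstate maintenance if patients losing control leave, is unbiased if leaving is unrelated to A1C, and understates maintenance if improving patients leave. With an SD of change of 0.8, a true rise of 0.20, 5 to 17% loss after week 24 and moderate to strong dependence, the understatement of the rise is about 0.01 to 0.08 A1C points, within a 95% CI half-width of about 0.15. These inputs are assumptions, and other values would change the size.

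It would also be too strong to infer that a repeated-measures model cures the problem. It does so when leaving depends on recorded A1C. When most leavers go before week 36 it removes about half the bias, so a sensitivity analysis is needed as well. The primary week-24 comparison is not affected by this point.

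**What to change.** Replace the durability sentence in the Efficacy Analysis Plan with:

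> The mean change in A1C from week 24 to week 44 in each arm, with its 95% CI, will be estimated as a contrast from a mixed model for repeated measures including A1C at weeks 12, 24, 36 and 44 from all mITT patients, with arm, visit, arm-by-visit, baseline A1C and baseline-by-visit, and unstructured covariance.

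In addition:

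- Keep the t-test in patients with both values as a supportive analysis.
- Add a sensitivity analysis in which patients who leave after week 24 are assumed to worsen, with the amounts of worsening fixed in advance.
- Report losses after week 24 by arm and reason.

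The cost is SAP wording, one further model with its sensitivity analysis, and one table. The A1C values come from scheduled visits, so no visits or patients are added. The downside is that the model assumes missing values are predictable from observed A1C, and the durability it reports may be slightly less favourable.
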